Our preliminary data has shown: (1) elevated blood cytokine concentrations during the acute phase of trauma are correlated with the development of fatal post-traumatic complications, (2) that early administration of a non-steroidal anti-inflammatory drug (NSAID) resulted in decreased blood serum levels of IL-6, Prostaglandin E2 (PGE2), improved pulmonary edema, and enhanced arterioles ability to vasoconstrict in response to hemorrhage in animal models, and (3) that the addition of the internal physiologic parameters (inflammatory cytokines) to New Injury Severity Score (NISS – a marker of the external anatomical insult) significantly improves the ability to predict hospital length of stay of trauma patients when compared to NISS alone. Our group is the first to use an integrative approach that combines the external anatomic injury data with the internal physiologic response for accurate prediction of patient's clinical outcome. Therefore, if we apply this same mindset to treatment, we can improve the trauma patients' care by addressing both parameters as opposed to solely focusing on the external injury as done in the past. Our ability to modify post-traumatic physiologic response via short-term administration of a NSAID may lead to improved patient outcome.

Over the last decade, clinicians remain puzzled over the safety of NSAID administration after fracture in terms of bone union. In addition, given the current landscape for opioid epidemic in the United States, alternative non-opioid pain management during acute trauma has the potential to reduce opioid consumption and represents a pivotal component of multimodal analgesia strategy.

5. Inclusion and Exclusion Criteria

Inclusion Criteria

- Patient aged 18-75
 - a. Patient or legally authorized representative (LAR) able to provide consent.
 - b. Patient with New Injury Severity Score (NISS) > 9 at time of admission determined by trauma staff.
 - c. Anticipated admission \geq 5 days

Exclusion Criteria

- d. Patient age < 18 or > 75
- e. Patients with injury more than 24 hours prior to evaluation
- f. Hemorrhagic shock or risk of significant hemorrhage.
- g. Patients with preexisting inflammatory medical condition such as inflammatory arthropathy or inflammatory bowel disease
- h. Patients with acquired immunodeficiency syndrome (AIDS)
- i. Patients who are pregnant
- j. Patients with active GI bleed or ulceration

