Group-level summary statistics will be calculated for demographic and clinical variables, and differences between the 2 groups will be evaluated using two-sample t-tests for quantitative measures and Fisher exact tests for categorical measures, as appropriate. LOS and MME values will be summarized using medians and interquartile ranges for each group. Group-level VAS pain scores will be summarized using means and standard deviations. An analysis of variance model will be fit to compare log-transformed LOS between the 2 groups. Linear mixed models will be used to estimate differences in VAS pain scores and log-transformed MME values over time between the 2 groups. Time and group comparisons for each cytokine will be made using linear mixed models, with and without adjusting for selected covariates. Patient demographic variables will be considered for inclusion as covariates in each model but will only be retained if they significantly improve the model. Linear mixed models may be log-transformed, double-log-transformed, or square-root-transformed to correct for right skewness, as appropriate. Likelihood ratio testing and Akaike information criterion will be used to select appropriate covariance structures in each case. A Kenward–Roger adjustment will be used to correct for negative bias in the standard errors and degrees of freedom calculations. Throughout the study, a P value of less than 0.05 will be considered significant. All analyses will be completed in SAS 9.4 (SAS Institute Inc.; Cary, NC).

8. Study-Wide Recruitment Methods

Potential patients will be prospectively identified either at the time of the initial consultation, at the morning fracture conference, based on the orthopaedic injury diagnosis (inclusion criteria noted above). Patients will be screened by their inclusion and exclusion criteria and will be considered for enrollment in the study should they meet study criteria.

9. Study Timeline

After arrival, patient screening and enrollment is expected within 12 hours of arrival to ensure initial blood draw. Further participation of subjects will include blood draws and ketorolac administration through day 5. Patient participation will continue through to their follow-up visits and conclude with their 6 weeks post discharge clinic visit. Detailed project timeline and schedule of activities is listed in Table 1.

Tentative time table of the proposed project												
Procedures	Enrollment	Inpatient						Outpatient				

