		Day 1	Day 2	Day 3	Day 4	Day 5	Discharge	2 Week	6 Week	3 Month	6 Month	12 Month
Inclusion/Exclusion Review	X											
Informed Consent	X											
Blood Sample		X	X	X	X	X						
Ketorolac Intervention		X	X	X	X	X						
MME		X	X	X	X	X	X					
VAS		X	X	X	X	X	X	X	X	X	X	X
Post-Traumatic Complications		X	X	X	X	X	X	X	X	X	X	X

10. Procedures Involved

- Patient identification:** Patients will be identified on morning intake rounds by the trauma team and the research staff who are present daily to screen and enroll patients.
- Screening/Enrollment:** Study population will consist of 112 patients (56 control, 56 treatment) admitted to the inpatient surgical service at University of Kentucky (UK) level I trauma center for management of trauma care. Trauma patients that are between the ages of 18-75 and with NISS > 9 (moderate injury) with anticipated admission of ≥ 5 days (to ensure completion of the treatment) will be enrolled (Grisoni et al., 2001; Stevenson, Segui-Gomez, Lescohier, Di Scala, & McDonald-Smith, 2001). All patients will be initially treated according to the standard Advance Trauma Life Support (ATLS) protocol and standard ICU protocols (if applicable). Experienced clinical research staff will prospectively identify patients who meet the inclusion criteria and none of the exclusion criteria detailed in table 2.
- Randomization:** Consented patients will be randomized using a computer-generated algorithm to the control group (1-2 mL of intravenous saline every 6 hours for 5 days after admission) or treatment group (15 mg of intravenous ketorolac every 6 hours for 5 days after admission).
- Treatment:** Ketorolac (15 mg) has been chosen as the treatment of choice for several reasons:
 - Ketorolac has a similar pharmacodynamics profile as indomethacin, which was used

in our previous animal model (Xiang et al., 2012).

(2) It is readily available intravenously obviating limitations of oral intake.

(3) In numerous prospective clinical studies, ketorolac infusion produced no change in cardiac or hemodynamic parameters in patients undergoing major vascular surgery (Camu, Van Overberge, Bullingham, & Lloyd, 1990; Peirce, Fragen, & Pemberton, 1990).

(4) 30 mg is the approved dose that is consistent with United States Food and Drug Administration (FDA) labeling per the package

(5) Ketorolac is part of the routine trauma acute pain protocol

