Patients with pre-existing medical co-morbidities and contraindications to ketorolac will be excluded from the study (see 5 for detailed exclusion criteria)

Patients in the treatment group will receive 15 mg IV ketorolac every 6 hours for 5 days after admission.

e. **Post-operative inpatient care:** Enrolled patients will have daily blood samples (10 cc) will be collected post-admission and at 24 hours intervals for 5 days by blinded health care personnel. The initial blood sample will be collected within 12 hours of initial injury and before the first scheduled administration of ketorolac to establish baseline cytokine profile. Subsequent blood sample collection will be 24 hours apart. Medication compliance and monitoring will be performed daily by the same research coordinators.

Sandwich ELISA will be used to determine the concentrations of IL-1, IL-6, IL-10, and PGE2 in obtained blood samples. Blinded quality control samples will be included in every batch for each ELISA assay. This will allow for the calculation of coefficient of variation (CV) within and across patient cohorts. In the present study, the CV will be calculated for IL-1, IL-6, IL-10, and PGE2. If wide variations are observed among the analytes during the analysis, we will restrict our analysis to analytes in which the CV is less than 20%.

In addition to the standard trauma labs (Sodium, Potassium, Creatinine, Lactic acid, Glucose, Platelet, blood urea nitrogen (BUN), hematocrit, and white blood cell count), patient demographics (sex, age, and BMI), injury data (mechanism of injury, NISS, and types of surgical/procedural interventions), posttraumatic complications (occurrence of bacterial pneumonia, ARDS, SIRS, MODS), complications defined in the National Trauma Dataset, and inflammatory data will be collected. This data will be maintained in our clinical database (REDCap) by a full-time Clinical Study Coordinator.

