Although ketorolac is part of the routine trauma acute pain protocol, the cost of the study medication (ketorolac) will be paid for by either an internal or external grant. All other treatment costs are within the standard of care and the expenses will be paid for by the patient and their health insurance. There is no additional post-operative follow-up required for this study beyond the surgeon's standard follow-up routine. There will be no financial compensation in return for participation in this study. The cost to analyze and collect the specimens for analysis will also be covered by the internal or external grant.

26. Consent Process

Consent and/or Authorization by a Legally Authorized Representative (LAR)

Eligible patients will be approached for their consent to participate. Informed consent will be obtained prior to the collection of any study related data. To encourage a high level of participation from eligible patients, the attending surgeon may be involved in the consent conversation. The research coordinator and surgeon may initiate the conversation together.

By virtue of the types of injuries studied (resulting from high energy mechanisms such as high-speed motor vehicle crashes, high falls, and blast injuries) it is expected that a large proportion (> 30%) to have an associated traumatic brain injury which may render them unable to provide consent for the study. It will be important not to exclude these patients from the study, as it would significantly reduce our ability to produce generalizable knowledge. These patients are at no greater risk of adverse consequences by virtue of their participation in the study and should be given the same opportunity to participate.

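### The 12-hour-from-injury rule for the baseline cytokine sample conflicts with the eligibility and enrolment windows, and the cytokine models do not account for time since injury

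*Combined protocol and SAP*

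**What the plan says.** Several parts of the protocol bear on when the first cytokine sample is taken.

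- **Section 5, exclusion (e)** removes "Patients with injury more than 24 hours prior to evaluation". Anyone from 0 to 24 h is therefore eligible on this criterion. Evaluation is not defined.
- **Section 9** says that "patient screening and enrollment is expected within 12 hours of arrival to ensure initial blood draw". The clock here starts at arrival.
- **Section 10(e)** says: "The initial blood sample will be collected within 12 hours of initial injury and before the first scheduled administration of ketorolac". The clock here starts at injury. The same item describes the daily samples as "collected post-admission and at 24 hours intervals for 5 days by blinded health care personnel", and adds: "Subsequent blood sample collection will be 24 hours apart".
- **Section 26** says: "Informed consent will be obtained prior to the collection of any study related data". The study draw therefore cannot come before consent.
- **Section 10(a)** says: "Patients will be identified on morning intake rounds by the trauma team and the research staff". Sections 8 and 23 also allow identification at the initial consultation and on presentation to the emergency department.

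Section 7 analyses each cytokine with a linear mixed model in time and group, with and without covariates. The only candidate covariates it describes are demographic, and they stay only if they significantly improve the model. Time since injury is not named. No section says how a late or missing baseline is handled, or ties Day 1 to the time of injury. Section 10(e) does not list the time of injury among the injury data, although exclusion (e) cannot be applied without it.

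**The concern.** Aim 1 asks whether early ketorolac dampens the inflammatory cascade. That cascade starts at the injury, so the meaning of a cytokine value depends on hours since injury. The plan has three timing rules on different clocks, and the strictest cannot hold for every patient the others admit. Section 9 offers its window as the safeguard for the draw, but that window secures the 12 h limit only if arrival coincides with injury.

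The first sample serves as the baseline, and the later samples are timed from it. A late first draw therefore either leaves the patient without a protocol-compliant baseline or shifts all five nominal days. The plan provides for neither case. The cytokine concentrations are the first listed secondary outcome and the mechanism named in the title, so their time profile should be readable.

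**Working it through.** **The plan's own figure.** The only computed design figure is the sample size for length of stay (Section 6), and it reproduces. With the normal approximation, n = 2 × (1.960 + 0.842)² × 1.5² / 0.928² ≈ 41.01, rounded up to 42 per group. The two-sample t-test with 42 per group has 80.0% power, and 84 / 0.75 = 112. It does not depend on sample timing.

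**Step 1: the three clocks.** Let A be hours from injury to arrival and D hours from arrival to first draw. Section 10(e) requires A + D ≤ 12, so D ≤ 12 − A. Section 9 expects enrolment with D up to 12, which implies A + D ≤ 12 only when A = 0. A patient arriving 4 h after injury has 12 − 4 = 8 h left; a patient first evaluated 13 h after injury has none. Exclusion (e) admits both.

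**Step 2: upper bounds.** If evaluation in exclusion (e) means arrival, the latest first draw within the expected windows is 24 + 12 = 36 h. If it means the research screening itself, the bound is about 24 h. Both exceed 12 h.

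**Step 3: post-injury age by nominal day.** Later draws are 24 h apart, so Day d adds 24 × (d − 1) h to the first-draw time.

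| Reading | Day 1 | Day 2 | Day 5 |
|---|---|---|---|
| 12 h rule enforced | 0–12 h | 24–36 h | 96–108 h |
| Not enforced, 24 h bound | 0–24 h | 24–48 h | 96–120 h |
| Not enforced, 36 h bound | 0–36 h | 24–60 h | 96–132 h |

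The ranges for adjacent days overlap only in the last row, by 36 − 24 = 12 h.

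**Step 4: share missing the 12 h limit.** The documents give no arrival times, so every distribution here is an assumption. Evaluation is taken to mean arrival, and A is limited to 0–24 h. The shares come from 1,000,000 simulated draws of A + D; counts are out of 112.

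| Assumed A | D uniform 0–12 h | D uniform 0–6 h |
|---|---|---|
| Exponential, mean 1 h | 8% (9) | under 0.1% (0) |
| Exponential, mean 2 h | 17% (19) | 2% (2) |
| Exponential, mean 4 h | 32% (35) | 11% (13) |
| Exponential, mean 8 h | 49% (55) | 30% (33) |
| Uniform 0–24 h | 75% (84) | 62.5% (70) |

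Hand check for D uniform on 0–12 h: the share is E[min(A, 12)] / 12. For A uniform on 0–24 h, E[min(A, 12)] = 0.5 × 6 + 0.5 × 12 = 9, and 9 / 12 = 75%. For an exponential with mean 1 h it is about 1 / 12 = 8%.

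**Step 5: spread of Day 1 age.** With D uniform on 0–12 h, the SD is √(Var A + 12²/12). For A exponential with mean 1 h this is √(1 + 12) = 3.6 h. For A uniform on 0–24 h it is √(48 + 12) = 7.7 h.

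**The case against.** The strongest reply is that the effect may be very small. If most patients arrive within an hour or two and are sampled within 6 h of arrival, at most about 2% miss the limit. Sections 8 and 23 support prompt identification, so morning rounds need not be the bottleneck. This stands. A reader might infer that many eligible patients cannot be sampled in time, but without arrival data the documents support no such statement.

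Other stronger readings also fail:

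- **That the plan permits 36 h.** No passage states this figure. It combines a limit on evaluation with an expectation counted from arrival, and holds only if the two events coincide.
- **That one patient's Day 1 is another's Day 2.** This needs first draws at least 24 h apart, which only the extreme end of the ranges allows.
- **That lost baselines and mixed days both accrue.** They are largely alternatives. Enforcing the 12 h rule keeps Day 1 within 0–12 h, and the mixed models can still use later samples from patients without a valid baseline.
- **That the time-by-group comparison must be blurred.** If a marker decays at a constant rate, a timing offset is the same constant on the log scale on every day. It is then between-patient variance, which a suitable covariance structure can absorb. Distortion of within-patient change needs other kinetics, for which the documents give no figures.
- **That treatment was not in fact early, or that the arms differ systematically.** No document reports delivered timing, and randomisation balances time since injury in expectation.

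None of this removes the contradiction between Sections 5, 9 and 10(e), the lack of a rule for late or missing baselines, or the absence of time since injury from Section 7.

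**Conclusion.** The conflict is certain because it follows from the text alone: a patient first evaluated more than 12 h after injury meets exclusion (e) but cannot meet Section 10(e). Its practical size is unknown, with a share from near 0% to 75% under the assumed arrival and draw times.

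If the rule is enforced, the cost is missing valid baselines. If it is not, Day 1 spans up to about 24 h after injury, or 36 h at most if evaluation means arrival, and the offset persists to Day 5. Either way the harm is confined to the secondary cytokine outcome, as lost precision and a time profile that is harder to interpret. No bias between arms is expected. The primary outcome, length of stay, and its sample size are unaffected. The point is modest but worth correcting, because the repair is cheap.

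**What to change.** 1. **Reconcile Section 5 exclusion (e), Section 9 and Section 10(e) to one clock**, and define evaluation. The screening comments in the IRB application say that enrolment is closed, so this clarifies the record and the reporting but cannot change past sampling. The analysis steps below are what can still help.
2. **Amend Section 7.** Prespecify hours from injury to the first, pre-dose sample as a fixed covariate in every cytokine mixed model, exempt from the significance-based retention rule. Alternatively, use actual hours since injury as the time axis. The covariate should be called pre-dose and not pre-randomisation, because Section 10(e) requires only that the draw come before the first scheduled dose.
3. **State the rule for late and missing baselines.** Keep patients with a late first sample in the main analysis. Where there is no pre-dose sample the covariate is undefined, so the plan must say how such patients enter the model; the time-axis option avoids this difficulty.
4. **Report injury-to-first-sample hours by arm.**
5. **Add a sensitivity analysis** limited to patients whose first sample fell within 12 h of injury. Select on sample time and not on dose time, since dose time falls after randomisation.

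The cost is one degree of freedom per model, plus retrieval of injury and draw times. Those times are assumed to be available: exclusion (e) could not have been applied without the injury time.

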Aim 2: Determine whether patients who received Ketorolac treatment require less opioid medication throughout their hospital and post-operative course. The outcome variable will be patient's subjective pain scores, morphine milligram equivalent intake along with other pain modulating medication intake. Inpatient and outpatient subjective pain reports will be collected and analyzed for pain relief and medication use.

Study Design

Describe and explain the study design (e.g., observational, secondary analysis, single/double blind, parallel, crossover, deception, etc.).

- *Clinical Research:* Indicate whether subjects will be randomized and whether subjects will receive any placebo.
- *Community-Based Participatory Research:* If you are conducting [community-based participatory research \(CBPR\)](#), describe strategies for involvement of community members in the design and implementation of the study, and dissemination of results from the study.
- *Qualitative research:* Indicate ranges where flexibility is needed, if a fixed interview transcript is not available, describe interview topics including the most sensitive potential questions.
- *Research Repositories:* If the purpose of this submission is to establish a Research Repository (bank, registry) and the material you plan to collect is already available from a commercial supplier, clinical lab, or established IRB approved research repository, provide scientific justification for establishing an additional repository collecting duplicate material. Describe the repository design and operating procedures. For relevant information to include, see the [UK Research Biospecimen Bank Guidance](#) or the [UK Research Registry Guidance](#).

This study is a double blinded, randomized, prospective, and multi-specialty collaborative clinical trial to assess the effect of early administration of Ketorolac as a preventative treatment for the post-traumatic complications associated with the hyperinflammatory response in trauma patients. The second objective is to determine whether patients randomized to ketorolac treatment require less opioid analgesics during their hospital and postoperative course than the standard of care (SOC). Please see protocol for full description of study design.

Attachments

Subject Recruitment Methods & Advertising

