Aim 2: The enrolled patients will be followed daily by our trained clinical research coordinator. Patient's subjective pain scores will be assessed and documented by the trained nursing staff using Visual Analogue Scale (VAS) daily. Morphine milligram equivalent (MME) along with other pain medication intake will be recorded per day for the duration of Ketorolac or placebo therapy. Patient's clinical course will be monitored closely and daily to ensure no NSAIDs will be administered to the control cohort to ensure consistency and protocol adherence of the study. Once patients are discharged from the hospital, outpatient pain scores will be assessed during routine clinic follow up visits using Patient-Reported Outcomes Measurement Information System (PROMIS) surveys. Opioid and pain modulating medication prescription refills will be monitored using the State All Scheduled Prescription Electronic Reporting system. Patient narcotic requirement will be assessed during all of the routine follow up visits by the same research coordinator in order to maintain consistency. Patients' inpatient and outpatient subjective pain score and MME intake will be compared between the control and treatment groups using two-tailed independent t-tests.

Aim 3:

Finally, analysis will be performed to evaluate the treatment effects between two groups using fracture unions as a dependent variable. The rate of fracture unions will be calculated at 3 month, 6 month and 12 month. Fractures will be considered united if they met the criteria for clinical or radiological union. The baseline clinical factors that are independently associated with fracture unions will be assessed from candidate variables and are entered using a forward ($p<0.05$) and backwards ($p<0.10$) stepwise selection procedure. Finally, the multivariate model will be performed to assess the association of clinical factors with fracture unions starting at 3 month between two groups.

Attachments

Data Collection & Research Materials

In this section, please provide the following:

- Describe all sources or methods for obtaining research materials about or from living individuals (such as specimens, records, surveys, interviews, participant observation, etc.), and explain why this information is needed to conduct the study.
- For each source or method described, please list or attach all data to be collected (such as genetic information, interview scripts, survey tools, data collection forms for existing data, etc.).

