Interventional Model Description: Compare the effectiveness of a NSAID to placebo in acute trauma setting.

Masking: Triple (Participant, Care Provider, Investigator)

Masking Description: Participant medical team will be blinded to the treatment or placebo intervention.

3. Outcome Measures

Primary Outcome: Length of Hospital Stay

Secondary Outcomes:

- Daily Concentrations of IL-1, IL-6, IL-10, and PGE2
- Incidence of Post-Traumatic Complications (e.g., bacterial pneumonia, SIRS, MODS, ARDS, and AKI)
- Mortality
- Visual Analogue Pain Scores
- Inpatient Morphine Milligram Equivalents
- Change in Inpatient Subjective Pain Reports
- Change in Outpatient Subjective Pain Reports

4. Background

Accidental trauma is the 4th leading cause of death in the United States, and it is associated with a complex inflammatory response. This response is associated with post-traumatic complications such as multi-organ dysfunction syndrome (MODS), bacterial pneumonia, acute respiratory distress syndrome (ARDS), systemic inflammatory response syndrome (SIRS), and post traumatic pain (PTP). It is unknown whether early modulation of inflammatory cytokines is associated with improved patient outcomes, reduced narcotic requirements, and improved patient subjective pain after hospital discharge.

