Enrolled patients will be monitored daily by research staff throughout their hospital stay and routine outpatient clinic visits. Patient's subjective pain scores will be assessed and documented by the trained nursing staff using Visual Analogue Scale (VAS) daily. Pre-injury narcotics use along with other pain modulating medication intake will be recorded per day in morphine milligram equivalent (MME) for the duration of ketorolac or placebo therapy in our password protected database. Patients' clinical course will be monitored closely and daily by research staff to ensure no NSAIDs will be administered to the control cohort to ensure consistency and protocol adherence. After patient discharge, various patient surveys will be used to assess patient pain, function, and quality of life. Opioid and pain modulating medication prescription refills will be monitored using State Scheduled Prescription Electronic Reporting System. Patient narcotic requirement will be assessed during all the routine follow up visits by the same research staff to maintain consistency.

11. Data and Specimen Banking

Blood sample specimens obtained from the research subjects will be labeled with the patient's unique study ID number and will be stored in the CCTS lab until analysis. Following analysis, the specimens will be disposed of in accordance with UK policies. No specimens will be retained for future studies. The stored de-identified data from the study will be kept for a minimum of 6 years for records in the event follow-up studies are pursued and will remain protected and encrypted. Data will be permanently

deleted following this time period. The banked data will be stored on a password-protected research drive. Upon conclusion of the study, the data will be stored in a password encrypted file that only the PI has access to.

12. Data Management

Following initial enrollment, each patient will be assigned a unique patient identifier. All electronic documentation containing total morphine equivalents, specimen results, and all other medical information will be associated with this unique patient identifier during analysis. All protected health information will be stored in a separate, password-protected research file that will not be accessed regularly. Following our secondary analysis, all personal health information will be removed from our electronic files and destroyed in accordance with patient privacy guidelines.

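### Daily MME stops with the 5-day therapy and post-discharge opioid data have no defined outcome or SAP analysis, so the plan supports an opioid conclusion for days 1–5 but not Aim 2's whole-course question

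*Combined protocol and SAP*

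**What the plan says.** **The question.** In the IRB application, Objectives, Aim 2 asks whether ketorolac patients "require less opioid medication throughout their hospital and post-operative course". The Study Design entry repeats this as the second objective. The numbered protocol, section 3, lists the secondary outcome "Inpatient Morphine Milligram Equivalents" with no day limit.

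**The recording rule.** The IRB application (Research Procedures, Aim 2) says that MME and other pain medication intake "will be recorded per day for the duration of Ketorolac or placebo therapy". Protocol section 10(e) has intake "recorded per day in morphine milligram equivalent (MME) for the duration of ketorolac or placebo therapy". Therapy lasts 5 days: "Patients in the treatment group will receive 15 mg IV ketorolac every 6 hours for 5 days after admission". Entry requires an anticipated admission of at least 5 days, "to ensure completion of the treatment".

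**The schedule.** Table 1 in section 9 marks MME on Days 1 to 5 and once at Discharge. None of the five outpatient visits has an MME mark, whereas the VAS row runs to 12 months.

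**After discharge.** Section 10(e) states: "Opioid and pain modulating medication prescription refills will be monitored using State Scheduled Prescription Electronic Reporting System". It also has staff assess narcotic requirement at routine follow-up visits, and the IRB application says the same. The IRB application further plans two-tailed t-tests on inpatient and outpatient MME. Section 3 lists outpatient pain reports but no outpatient opioid outcome. Section 7 plans a linear mixed model for log-transformed MME over time. It states no window and does not mention refills or outpatient narcotic requirement.

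**The concern.** The aim covers the stay and the period after it, but daily measurement ends when the study drug ends. A difference in MME over days 1 to 5 shows what happens while ketorolac is running. It cannot show whether opioid use is reduced overall or only deferred until the drug stops, and that is the distinction Aim 2 depends on. Protocol section 16 lists lower opioid dependence and usage among the potential benefits, which 5 days of inpatient records cannot address.

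Post-discharge data could fill part of the gap, but they have no defined unit, time window or model in the protocol's outcome list or analysis plan. Any outpatient opioid result would therefore rest on choices made after the data were in hand.

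**Working it through.** **The plan's own figures.** The only sample size is for length of stay (LOS), the primary outcome. With a difference of 0.928 days, SD 1.5, two-sided alpha 0.05 and 80% power, the standard two-means formula gives 42 per group. Exact noncentral-t power at 42 is 80.0%, and 84/(1 − 0.25) = 112. These reproduce but do not bear on this point. The documents give no power calculation for MME.

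**What is covered, by period**

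| Period | Data planned | Outcome in section 3 | Analysis in section 7 |
|---|---|---|---|
| Days 1–5 | Daily MME | Inpatient MME | Mixed model, log MME |
| Day 6 to discharge | No daily record; one undefined Discharge mark | Within the wording of inpatient MME | Window not stated |
| After discharge | Refills; narcotic requirement at visits | None for opioids | None |

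The Discharge mark could mean the last 24 hours, a cumulative inpatient total, or the discharge prescription. No section says which.

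**Share of inpatient days without MME.** Inputs are 5 daily records (therapy length, section 10) and an assumed stay of L inpatient days, because the documents give no mean or distribution of LOS.

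- Discharge mark adds no day: gap = (L − 5)/L.
- Discharge mark counts as one further day, for L of 6 or more: gap = (L − 6)/L.

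| Assumed L (days) | (L − 5)/L | (L − 6)/L |
|---|---|---|
| 5 | 0/5 = 0% | no gap |
| 6 | 1/6 = 17% | 0/6 = 0% |
| 8 | 3/8 = 38% | 2/8 = 25% |
| 10 | 5/10 = 50% | 4/10 = 40% |
| 12 | 7/12 = 58% | 6/12 = 50% |

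If the Discharge entry is a cumulative total, the inpatient sum is covered at every L. Even then, the daily pattern after therapy stops is not.

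**After discharge.** MME is scheduled at 0 of 5 outpatient visits. The end of follow-up is also unclear: the text of section 9 ends participation at the 6-week clinic visit, while its Table 1 runs to 12 months.

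**The case against.** A reader might infer that opioid use after day 5 is not measured at all. The documents do not support that. Table 1 has a Discharge entry, refills are tracked, and narcotic requirement is assessed at follow-up visits. Nor can one say that post-discharge data enter no analysis anywhere, since the IRB application plans an outpatient MME t-test. The supportable statement is that the protocol's outcome list and analysis plan do not carry it over.

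It is also tempting to say that most patients have unrecorded inpatient days. Eligibility rests on an anticipated stay of at least 5 days and no LOS data are given, so the statement can cover only patients who stay beyond day 5.

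A third tempting inference is that a 5-day result is already being presented as the whole-course answer. The interim abstract text in the continuation review ties its opioid result to the 5-day treatment period. Its conclusion omits the window but claims nothing about opioid use after discharge.

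The strongest defence of the design is that days 1 to 5 match exposure and are largely shared by all patients. Later inpatient days exist only for those still in hospital, and LOS is the primary outcome and may itself be affected by treatment. That stands, and it is why the later days should be descriptive. It is also true that the whole-course wording sits in the IRB application, and that the numbered protocol names only inpatient MME, as a secondary outcome. But inpatient MME is not limited to 5 days either, so the mismatch remains within the protocol.

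Finally, the sentence in section 10(e) literally has pre-injury narcotics use as its subject. The parallel sentence in the IRB application is the clearer statement of the rule, and it sets the same window.

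**Conclusion.** The point holds as a mismatch between the question and the planned data and analysis. As written, the trial can support a conclusion about opioid use on days 1 to 5, but not about the hospital and post-operative course as a whole.

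The inpatient gap is 17% to 58% of days for assumed stays of 6 to 12 days, 0% to 50% if the Discharge entry counts as one day, and nil at 5 days. These shares depend on the assumed stays and on the undefined meaning of the Discharge mark. They say nothing about how many patients are affected or about the direction of any bias. The post-discharge gap is one of definition and analysis, not of collection.

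This concerns a secondary aim and leaves the LOS comparison untouched. It should be corrected because the stated rule cannot separate reduced opioid use from delayed use.

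**What to change.** 1. In the IRB application (Research Procedures, Aim 2) and protocol section 10(e), record MME on each day until discharge, abstracted from existing medication records. Mark this in Table 1, say what the Discharge entry contains, and correct the subject of the sentence in section 10(e).
2. In section 7, state that days 1 to 5 are the main MME comparison. Report day 6 to discharge descriptively, with the number still in hospital each day.
3. Add to sections 3 and 7 a post-discharge opioid outcome over a fixed window, built from the refill data already monitored, with a stated unit and between-group analysis. Reconcile the 6-week and 12-month follow-up statements first, so that the window is clear. Carry over or withdraw the outpatient t-test in the IRB application.
4. If items 1 and 3 are not done, restrict Aim 2 and its conclusion to the 5-day treatment period, which is only a text edit.

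**Cost.** Items 1 and 2 need extra chart abstraction, which is retrospective because enrolment is closed. Refill data reflect prescriptions rather than intake, and refills are not the same as all opioid dispensed. Interim MME results by group already exist, so any added outcome should be dated and labelled as added after them.
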